## **8. TRIAL ASSESSMENTS**

### **8.1. Screening assessments**

The following screening assessments should be conducted prior to randomisation

- Complete history.
- DRE and physical examination (only if clinically indicated).
- Assessment of performance status, using WHO scale (see Appendix 1).
- Assessment of fitness using the Adult Comorbidity Evaluation (ACE-27) scale and American Society of Anaesthesiologists (ASA) scale (see Trial Guidance Notes).
- Eligibility for A vs B, and A vs B vs C1 vs D1:  
Radiological assessment of prostate cancer. Ideally within 2 months and within a maximum of 12 months prior to randomisation and 6 months prior to starting ADT; this includes a mpMRI scan of the prostate and pelvis and at least one of the following: bone scan, WB MRI, MRI spine, Choline PET, PSMA PET. If patients are longer than 6 months on ADT because of the COVID-19 pandemic, the imaging needs to be performed in 6 months prior to starting ADT.

PIVOTALboost arm B closed to recruitment in Q2 2022.

- Eligibility for A vs B vs C2 vs D2:  
Radiological assessment of prostate cancer. Ideally within 2 months and within a maximum of 12 months prior to randomisation and starting ADT; this includes a mpMRI scan of the prostate and pelvis and at least one of the following: bone scan, WB MRI, MRI spine, Choline PET, PSMA PET. If the patient is offered the boost randomisation arms (A vs B vs C2 vs D2) a **pre-biopsy mpMRI is mandatory**. If the pre-biopsy mpMRI has occurred more than 6 months prior to randomisation or starting ADT a repeat mpMRI is strongly recommended prior to treatment to exclude progressive disease in the interim. If patients are longer than 6 months on ADT because of the COVID-19 pandemic, the imaging needs to be performed in 6 months prior to starting ADT; a pre biopsy mpMRI remains mandatory. Please see definition of a suitable focal boost volume on page 16, Box 1.

PIVOTALboost arm B closed to recruitment in Q2 2022.

- PSA test prior to the commencement of ADT (as per eligibility criteria should be <50ng/ml)
- Full blood count, Urea & Electrolytes. For patients affected by the COVID-19 pandemic, results taken prior to or at planning are acceptable.
- Baseline symptoms will be assessed using Common Toxicity Criteria for Adverse Event Reporting (CTCAE) version 4.03 and RTOG bladder and bowel toxicity scoring (conducted within 4 weeks prior to randomisation).

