### **13.2. Treatment Allocation**

During the design of the study, it was acknowledged that recruitment and allocation into the different treatment arms could evolve during the trial, given the number of sites open, and the type of boost available at each site. We ran simulations to explore how this would affect time to complete overall recruitment. Following this, we decided to start the trial using an allocation ratio of 2:2:3:3, so it favours the boost groups C or D in a period where it is expected less sites would be offering the boost treatment groups. The allocation ratio may be adjusted during the trial to ensure 9:9:8:8 final relative numbers. Recruitment will be closely monitored and allocation ratios will be monitored annually. On completing recruitment to AvB comparison, the treatment allocation will be 1:1:1 A:C:D.

Full details on the allocation ratio and simulation study will be provided in the Statistical analysis Plan.

Treatment allocation is by minimisation with a random element; balancing factors will be:

- Randomisation Option 1: centre, NCCN risk group (intermediate, high) and suitable volume for focal boost (yes/no).
- Randomisation Option 2a/2b: centre, NCCN risk group (intermediate, high), suitable boost volume for focal boost (yes/no), type of boost (whole gland HDR, focal HDR or focal IMRT) – the last 2 factors will be combined to obtain excluding categories.

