### **13.6. Analysis plan**

The principal analysis will occur after a median follow-up of five years or the target numbers of events have been reached, whichever occurs first. A total of 820 events (217 events x 2 (A, B) + 193 events x 2 (C, D)) to detect a difference of 7% with 85% (A vs B) or 80% (A vs C, D) power is required. Should the analysis not be event driven, the timing will be subject to approval from the IDMC.

The primary comparisons will compare each of the experimental arms to the standard (i.e. A vs B, A vs C and A vs D) and will include all randomised patients (intention-to-treat analysis). Only contemporaneously randomised controls will be used for the A vs C and A vs D comparisons. As secondary analyses, comparisons between experimental arms will also be reported, as well as the overall impact of prostate IMRT vs prostate and pelvis IMRT (A+C vs B+D) and no prostate boost vs prostate boost (A+B vs C+D). Exploratory analysis of the heterogeneity of treatment effect across whole gland or focal boosts, and type of focal boost (IMRT or HDR) will be performed.

All treatment effects will be presented with 2-sided 95% confidence intervals. Adjustment will be made for multiple testing as appropriate. Time to event endpoints will be summarised presenting estimated Kaplan-Meier curves (by treatment); the time point of primary interest is 5 years from randomisation, which will be presented with 95% CI for each treatment arm. Treatment effects will be estimated and tested for significance by the Cox proportional hazards model, adjusting by stratification factors.

Adjusted models will include the duration of ADT prior to starting radiotherapy (as a result of COVID19 related delays to radiotherapy starting). Further models adjusting by other important known prognostic factors will also be fitted. Methods to account for non-proportionality will be used if appropriate. Acute and late side effects will be summarised as frequencies and percentages at each time point. Acute toxicity will also be summarised as worst toxicity reported during radiotherapy. The proportion experiencing grade $\geq$ 2 side effects will be presented; comparisons between treatment groups will be tested using chi-squared or Fishers exact tests. Logistic regression models will be used to estimate treatment differences (odds ratios). Analysis of QL and health economic endpoints are further detailed in Section 20.

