Further details of analysis methods will be specified in a Statistical Analysis Plan in accordance with ICR-CTSU Standard Operating Procedures. The Statistical Analysis Plan will include a section to detail how data impacted by strategies introduced to mitigate risks relating to the COVID19 pandemic will be handled.

Any quality of life data collected from PIVOTALboost participants within the SPRUCE study will be shared with PIVOTALboost for analysis.

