### **A3. RTOG Toxicity Scales**

#### **Instructions**

1. Toxicity grade should reflect the most severe degree occurring during the evaluated period, not an average.
2. When two criteria are available for similar toxicities, the one resulting in the more severe grade should be used.
3. Toxicity grade = 5 if that toxicity caused death of the patient.
4. An accurate baseline prior to start of therapy is necessary.

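### Grade 2+ toxicity is tested without adjustment although pre-randomisation grades are in hand: valid, but some precision is given up and the approach differs from the FFS and quality-of-life analyses

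*Protocol*

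**What the plan says.** Section 13.6 treats the outcome types differently.

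- **Time-to-event endpoints:** "Treatment effects will be estimated and tested for significance by the Cox proportional hazards model, adjusting by stratification factors". One adjusted model gives both the estimate and the test.
- **Grade 2 or worse toxicity:** "comparisons between treatment groups will be tested using chi-squared or Fishers exact tests". The next sentence reads "Logistic regression models will be used to estimate treatment differences (odds ratios". Testing and estimation are thus assigned to different procedures, and covariates for the logistic model are neither listed nor excluded.
- **Quality of life (section 20.2):** changes from baseline are compared between arms by ordinal logistic regression or ANCOVA.

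The baseline data exist. Section 8.1 lists among the screening assessments: "Baseline symptoms will be assessed using Common Toxicity Criteria for Adverse Event Reporting (CTCAE) version 4.03 and RTOG bladder and bowel toxicity scoring", done no more than four weeks before randomisation. Appendix 3 adds: "An accurate baseline prior to start of therapy is necessary". In section 13.2, "Treatment allocation is by minimisation with a random element; balancing factors will be" introduces centre and NCCN risk group, and for the boost options "suitable boost volume for focal boost (yes/no), type of boost (whole gland HDR, focal HDR or focal IMRT".

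Section 2.1 puts comparable bladder and bowel side effects into the primary objective. Section 4.2 lists toxicity as a secondary endpoint, and FFS is the only primary endpoint.

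**The concern.** A two-by-two test cannot use the screening grade or the minimisation factors. Acute RTOG bladder grade 2 (Appendix 3) is defined by urinary frequency as such, not only by change from the patient's own habit. Symptoms present before treatment can therefore count towards grade 2 or worse at week 18. To that extent the count carries between-patient variation unrelated to the allocated arm, and a model with the screening grade could remove part of it.

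This has some practical weight because an arm with better FFS is meant to be judged also on whether its side effects are comparable to those of arm A. When the hoped-for answer is no excess, a less sensitive test leans towards that answer. It is also hard to explain why clinician-graded toxicity alone has a named test that uses neither baseline nor balancing factors.

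**Working it through.** **The protocol's own toxicity figures.** The only toxicity sizing is the interim check in section 13.7: 20% expected, 30% to be ruled out, one-sided 5%, 80% power, 119 patients per arm. An exact binomial search gives n = 119 as the smallest solution, accepting up to 27 events: P(X ≤ 27 | 0.30) = 0.048 and P(X ≤ 27 | 0.20) = 0.804. The sample size reproduces. (Section 13.7 triggers the review at 27 or more; that boundary is a separate matter.) No power or margin is stated for the between-arm toxicity tests.

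**Inputs.**
- Arm sizes from Appendix 4: A = 144 + 246 = 390; C = 212 + 246 = 458.
- Control rate 20% (section 13.7).
- Assumed, not in the protocol: comparison rate 27%, two-sided 5%, and the correlation ρ between screening grade and later grade 2+ toxicity.

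**Formula.** Adjustment for a baseline variable with correlation ρ cuts the variance by about 1 − ρ²:

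SE² = [p0(1 − p0)/390 + p1(1 − p1)/458] × (1 − ρ²); power ≈ Φ(|p1 − p0|/SE − 1.96).

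For 20% vs 27% with ρ = 0: SE² = 0.16/390 + 0.1971/458 = 0.000841, SE = 0.0290, 0.07/0.0290 = 2.41, power = Φ(0.45) ≈ 0.675.

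| ρ | 20% vs 27% | 20% vs 30% |
|---|---|---|
| 0 (unadjusted) | 67.5% | 92.4% |
| 0.2 | 69.3% | 93.4% |
| 0.3 | 71.6% | 94.5% |
| 0.4 | 75.0% | 95.9% |
| 0.5 | 79.6% | 97.5% |

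**What these correlations require.** Take a yes/no baseline symptom and 23.5% average toxicity. With 20–40% of patients symptomatic at screening, an odds ratio of 3 for later toxicity gives ρ of about 0.21–0.23, and an odds ratio of 6 gives about 0.35–0.36. At 5–10% prevalence the same odds ratios give only 0.12–0.17 and 0.21–0.28. So 0.2–0.3 is a moderate assumption, 0.4 a strong one and 0.5 optimistic.

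**Check by simulation.** 3,000 trials per scenario compared the chi-squared test with the Wald test from a logistic model containing the baseline symptom (two-sided 5%; prevalence and odds ratio assumed).

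| Scenario | Unadjusted | Adjusted, OR 3 (prevalence 5–20%) | Adjusted, OR 6 (prevalence 20–40%) |
|---|---|---|---|
| A 390 vs C 458, 20% vs 27.5% | 72–74% | 74–75% | 78–79% |
| A 517 vs B 517, 20% vs 27% | 75–76% | 76–78% | 81–82% |
| 517 vs 517, 5% vs 9.5% | 80–81% | 80–81% | 82–83% |

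With an odds ratio of 1 there was no gain. Overall the gain was about 0–2 points at odds ratio 3 and about 1–6 points at odds ratio 6.

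**Rare events.** At about 4% toxicity (section 1.1.4 cites grade 2+ lower GI rates of 3.3% and 4.8% at 18 weeks in the earlier phase II trial), odds ratios of 3–6 give ρ of only 0.07–0.19. That is a variance reduction of roughly 0.5% to 4%, which is negligible.

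**The case against.** The strongest reply is that this is detail for the analysis plan: "Further details of analysis methods will be specified in a Statistical Analysis Plan", the logistic model is already promised, its covariates are open, and section 13.6 attaches confidence intervals to all treatment effects. That stands for the covariate list. It does not cover the test, which the protocol has already named; a plan that tested by adjusted logistic regression would depart from it.

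Several further points also stand and limit the size:

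- The unadjusted test is valid under randomisation, and at worst slightly conservative under minimisation. A reader might infer that the toxicity p-values are wrong or biased; nothing in the protocol supports that.
- A reader might also infer that chance imbalance in baseline symptoms must pass into the treatment estimate. The estimate comes from the logistic model, whose covariates are not fixed here, so that does not follow.
- Exclusion criterion 11 keeps out conditions that make radiotherapy inadvisable, with inflammatory bowel disease and marked urinary symptoms as examples. This limits how common baseline symptoms can be.
- The minimisation factors are centre, disease risk and boost features. No section shows that they predict toxicity, so no extra gain can be claimed for them; the reason to include them is consistency with the allocation method.
- Fisher's test has a proper use when events are as sparse as the cited GI rates.

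**Conclusion.** The point holds as one of efficiency and consistency, not as an error. Section 13.6 fixes a test that leaves unused a baseline measure the trial collects before randomisation. At 20% vs 27% with 390 and 458 patients, power of about 68% would become about 69–72% at ρ = 0.2–0.3 and about 75% at 0.4. At the protocol's own 20% vs 30% it would move from about 92% to 93–96% over the same range, and for rare events or a non-predictive baseline hardly at all.

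These figures rest on an assumed correlation, an assumed 27% comparison rate and a two-sided 5% level. None of the three is stated for the toxicity tests.

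Two stronger readings should be resisted. Toxicity is not half of a co-primary test: it appears in the wording of the primary objective, but FFS is the sole primary endpoint. Nor can the lost precision be called large, since a gain of five points or more at 20% vs 27% needs a correlation of about 0.35 or higher.

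**What to change.** Amend the toxicity sentence in section 13.6 so that test and estimate come from one model. Suggested content: grade 2 or worse toxicity at week 18 and at each late visit is compared by logistic regression, adjusted for the patient's screening grade for the same organ on the same scale and for the minimisation factors of the patient's randomisation option (centre, if numerous, as a random effect). Report the odds ratio and a standardised risk difference, each with its confidence interval; the risk difference is useful because a covariate-adjusted odds ratio is not directly comparable with a crude one. Chi-squared or Fisher tests remain as unadjusted support, and as the test where events are too few to fit the model.

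Use the screening score and not the pre-treatment score of section 8.2. The latter is tied to radiotherapy planning, which under section 10.5 may follow the HDR implant, so it could already reflect allocated treatment.

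The cost is a wording change before the toxicity comparisons are analysed, carried through to the analysis plan. No new data, visits or patients are needed.

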### **13.7. Interim analyses and stopping rules**

Adherence to dose volume constraints will be checked after 30 patients are recruited to each experimental arm to ensure treatment can be delivered within safe constraints. Adherence to treatment will be monitored closely during recruitment: in particular any delays or interruptions of more than 5 days of treatment will be escalated to the Trial Management Group.

The IDMC will review emerging safety and efficacy data at regular intervals (at least annually).

Once 119 patients have been recruited to each of the experimental arms (B, C, and D) and completed their week 18 toxicity assessment an interim safety analysis will be conducted to rule out 30% (or more) patients with RTOG grade 2 or worse bladder or bowel complications. The figure has been estimated assuming an expected rate of 20% in the control group (inferred from data for all patients in the PIVOTAL study) and powered (80% power, 0.05 one-sided  $\alpha$ ) with a one-stage A'Hern design. If 27 or more patients out of 119 in one group developed bladder or bowel complications of grade 2 or more at 18 weeks, consideration will be given to modifying the trial design by dropping the treatment arm. As the recruitment pattern for arm B is different to arms C and D this analysis will be carried out as the data for each of the experimental arms matures.

No formal early stopping rule for futility or efficacy for the primary endpoint (FFS) has been planned.

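### The interim toxicity cut-off of 27 or more out of 119 is one too low for the stated design: power is 74%, not 80%, and an arm at the expected 20% rate is flagged 26% of the time

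*Protocol*

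**What the plan says.** Protocol section 13.7 (Interim analyses and stopping rules) fixes every element of the rule in one paragraph.

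- **Timing and size:** "Once 119 patients have been recruited to each of the experimental arms (B, C, and D) and completed their week 18 toxicity assessment".
- **Aim:** "an interim safety analysis will be conducted to rule out 30% (or more) patients with RTOG grade 2 or worse bladder or bowel complications".
- **Planning value:** "The figure has been estimated assuming an expected rate of 20% in the control group".
- **Error rates and method:** "80% power, 0.05 one-sided" alpha, "with a one-stage A'Hern design".
- **Action limit:** "If 27 or more patients out of 119 in one group developed bladder or bowel complications of grade 2 or more at 18 weeks", in which case "consideration will be given to modifying the trial design by dropping the treatment arm".

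The rule is applied to each of arms B, C and D as its data mature. The section gives no other numerical limit for dropping an arm, and it says that no formal futility or efficacy rule is planned for failure-free survival.

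**The concern.** In a one-stage exact design, the sample size, the two rates, alpha, power and cut-off are tied together. Once the first five are fixed, the cut-off follows. The printed limit looks like the largest acceptable count (27) written as the smallest unacceptable one.

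If so, the IDMC is working to a rule whose properties differ from those stated. It would believe that an arm performing as expected is flagged about one time in five, when the figure is about one in four. At exactly 27 events the text prompts a discussion of dropping an arm, although the powered design would conclude that 30% had been ruled out.

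**Working it through.** **Inputs (all from section 13.7).** n = 119 per arm; unacceptable rate 30%; expected rate 20%; one-sided alpha 0.05; power 80%; printed flag at X ≥ 27, so the arm passes with X ≤ 26. X is the number of patients with grade 2+ bladder or bowel toxicity at 18 weeks.

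**Definitions.** If an arm passes with X ≤ c:

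- alpha = P(X ≤ c | n, 0.30), the chance of passing an arm at the unacceptable rate;
- power = P(X ≤ c | n, 0.20), the chance of passing an arm at the expected rate;
- false flag = 1 − power.

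All are exact binomial probabilities.

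**Step 1: reproduce the sample size.** The smallest n for which some c gives alpha ≤ 0.05 and power ≥ 0.80 is n = 119. The normal approximation agrees:

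n = [1.645 × √(0.3 × 0.7) + 0.842 × √(0.2 × 0.8)]² / (0.30 − 0.20)² = 118.9.

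So the protocol's 119 is right, and the hypotheses and error rates have been read as intended.

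**Step 2: find the cut-off that goes with n = 119.**

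| Flag at | Pass with | alpha | power | false flag at 20% |
|---|---|---|---|---|
| ≥ 26 | ≤ 25 | 0.0182 | 0.6587 | 0.3413 |
| **≥ 27 (printed)** | ≤ 26 | 0.0302 | 0.7366 | 0.2634 |
| **≥ 28** | ≤ 27 | 0.0478 | 0.8036 | 0.1964 |
| ≥ 29 | ≤ 28 | 0.0726 | 0.8587 | 0.1413 |

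Only the flag at 28 or more meets both stated error rates. One lower loses the power; one higher breaks alpha. In A'Hern's terms, at least 92 of 119 patients must be free of the toxicity, and 119 − 92 = 27 events are acceptable.

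**Step 3: try the other reading.** With the hypotheses reversed (null 20%, alternative 30%), the smallest n is 116 with a cut-off of 31. At n = 119 the cut-off would be 32, with power 0.798. That reading gives neither 119 nor 27.

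**Step 4: size of the difference.**

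- Shortfall from the stated power: 80.0% − 73.7% = 6.3 points.
- Difference between the two cut-offs at a true 20%: 0.8036 − 0.7366 = 0.067, the probability of exactly 27 events.
- The same difference at a true 30%: 0.0478 − 0.0302 = 0.018.
- At least one false flag over three arms, all at 20% and treated as independent: 1 − 0.7366³ = 0.60 for the printed rule, against 1 − 0.8036³ = 0.48 for the matching one.

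**The case against.** The arithmetic is hard to dispute; the case on the other side concerns how much it matters.

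- **The error is cautious.** The purpose is to rule out 30%. The printed rule does this at alpha 0.030, inside the stated 0.05, and flags an arm at 30% in 97.0% of cases instead of 95.2%. No participant is less protected. This stands.
- **The rule is not binding.** Crossing the limit leads to consideration of a design change, and the IDMC also reviews emerging data at least annually. A false flag is therefore not a dropped arm. This stands.
- **True rates may be below 20%.** Section 1.1.4 reports 18-week grade 2+ lower GI toxicity of 3.3% and 4.8% in the earlier pelvic-node trial. Section 1.1.8 reports that toxicity had largely resolved to grade 1 by 18 weeks in two focal-boost studies. At a true 15% the flag probability is 1.7% against 0.9%, and at 10% it is negligible under either rule. Those sources use a different endpoint or schedule, however, and 20% is the protocol's own planning value. The point limits the practical effect but does not reconcile the numbers.
- **The interims may be past.** Appendix A4 puts arms C and D at 212 patients each and arm B at 517 on February 2022 estimates, all well above 119. The protocol does not say whether the checks have been held, and nothing shows that the cut-off changed a decision.

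None of these makes the printed cut-off agree with the stated 80% power.

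**Conclusion.** The concern holds. The sample size of 119 is correct for the stated design; the action limit is off by one. As printed, the rule has one-sided alpha 0.030 and power 73.7%, and it flags an arm at the expected rate 26.3% of the time. The matching limit of 28 gives 0.048, 80.4% and 19.6%.

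These per-arm figures rest only on the inputs in section 13.7 and the exact binomial distribution with exactly 119 evaluable patients. The three-arm figures (60% against 48%) also assume that all arms sit at 20% and are independent.

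The practical consequence is modest, because the slip is conservative for safety, the rule is advisory, and the verdict changes at one count only. It is still a plain error in the only numerical criterion for considering dropping an arm, and it should be corrected.

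**What to change.** Reconcile the action limit in section 13.7 with the stated error rates, in one of two ways:

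1. state the limit as 28 or more out of 119 (more than 27), which delivers the stated alpha and power; or
2. keep 27 or more as a deliberately stricter trigger, and restate the design as one-sided alpha 0.03 with 74% power.

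Tell the IDMC which applies. Check whether any interim already held recorded exactly 27 events, the only count at which the two rules disagree, and re-read that result if so.

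While the paragraph is open, note that section 1.2.2 speaks of a minimum of 119 patients per arm. If an analysis uses more than 119, a fixed count no longer carries these error rates, so the text should say that the rule is applied to exactly 119 patients or give the limit for other denominators.

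The cost is one number in the protocol and a note to the IDMC. The sample size and conduct of the trial do not change.
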